14.2 Reproduction Risks: N/A

14.3 Risks to Others: N/A

15 Incomplete Disclosure or Deception

15.2 Incomplete Disclosure or Deception:

This study will not use incomplete disclosure or deception.

16 Potential Benefits to Participants

16.1 Potential Benefits: We anticipate that using the smartwatch technology will benefit participants by improving social interactions and well-being.

17 Statistical Considerations

17.1 Data Analysis Plan:

Phase I Quantitative Analysis: As the aim of Phase I is to examine the feasibility, acceptability, and utility of Smartwatch Reminder, the quantitative analyses of Phase I will largely rely on descriptive statistics. Specifically, Phase I quantitative analyses will utilize frequency tables and means to examine sample characteristics and item-level responses to the 18-item system review checklist and context of care items (see appendix). Mean scores for each item, as well as an overall summary score for each participant, will be calculated.

Phase I Qualitative Analysis: Analyses of qualitative treatment fidelity data will primarily focus on thematic content analysis of open-ended data to examine Smartwatch utility and mechanisms of benefit. As noted by experienced methodologists, systematic reading and rereading of qualitative content and hand coding of a significant proportion of this content is necessary in order to develop an understanding of meanings in their conversational or observational contexts(38, 39). Grounded theory techniques described by Morse(38) and Strauss and Corbin(39) will guide the analyses of qualitative data in this evaluation. These approaches allow participants to construct meanings, perceptions, and behaviors from their own vantage points. [name] and [name] will lead open-coding of all available qualitative data: the interview transcripts and RA field notes. All qualitative data will be thematically analyzed using Braun and Clarke's (2006) six steps of thematic analysis: (1) familiarization; (2) generation of initial codes; (3) search for themes; (4) review themes; (5) define and name themes; and (6) write up of themes analyzed. Researchers will follow an iterative process to continually identify themes, linkages, and explanations. Regular debriefing and audit trails (clear pathways detailing how the data are collected and managed) will enhance transparency and credibility(40). All open-ended data collected will be first read by [name] and [name] to identify textual elements that emerge repeatedly (i.e., codes); these codes will then be clustered into larger categories that are later used to construct major thematic elements from the text (with the use of nVivo 10 analytic software). These themes will provide insights as to the SR's implementation and use (i.e., treatment fidelity/process evaluation embedded component) and mechanisms of benefit (i.e., semi-structured interview embedded component). During weekly meetings in the analysis phase of the proposed project, [name] and [name] will discuss their own identified codes to reach a consensus about specific codes, categories, and themes that emerge from the qualitative data (these decisions will be noted in an

SOCIAL PROTOCOL (HRP-580)

PROTOCOL TITLE: A Mobile Informatics Solution to Aid in Memory

VERSION DATE: 7/1/2022

audit trail). In addition, patterns that link particular themes will be identified and discussed in successive meetings between [name] and [name] to identify more complex processes of Smartwatch use or this technology's pathways to benefit PWMC and their care partners. During monthly team meetings, the development of codes, categories, and themes will be reviewed with the other academic investigators (Drs. [name] and [name]) and the AME team to yield any additional input into these project components. The multiple team meetings and discussions will allow for an exploration of alternative interpretations of the qualitative data and will also provide a check regarding the quality and richness of the data collected during the embedded mixed methods components.

Phase II Quantitative Analysis: Data available at baseline and 6 months will allow for a 2x2 repeated measures analysis of covariance to examine whether use of the SR results in statistically significant changes in PWMC negative health transitions and , social interaction, pleasant events, social stress, loneliness, , relationship closeness, and community engagement and care partner well-being, such as social support, depression and burden (9). The primary independent variable in the proposed investigation consists of an indicator variable for random assignment into the SR treatment condition or the attention control group. IBM SPSS Statistics 21(41) will be used to conduct these analyses, as it supports a range of univariate, bivariate, and multivariate statistical analysis procedures. The team has extensive experience conducting longitudinal analyses on their prior research on dementia(5, 6, 42-44). Our proposed analyses will provide in-depth tests of the study hypotheses. Outcomes will include statistical significance of within-subjects, or 6-month change, in those in the Smartwatch Reminder treatment or control groups on key outcome variables (see above). Additional analyses will determine if covariates (context of care, mobile device proficiency, and dementia severity indicators) significantly vary across the SR treatment and attention control groups at baseline and over 6-months. If statistically significant variations between the SR treatment and control groups are found, baseline and/or change scores for these covariates will be included in all repeated measures analyses of covariance tests to provide additional statistical control.

Variations in SR use and setting: Empirical treatment fidelity data and context of care measures that assess heterogeneity in the use of SR within the treatment condition (e.g., frequency and duration of SR use) will be included as a series of additional analyses. These analyses will explore the effects of variations in SR use on the outcomes hypothesized above for PWMCs and their care partners.

Phase II Qualitative Analysis: The methods described in Phase I Qualitative Analysis will be applied to the open-ended system review checklist responses, as well as the interviews gathered at the end of Phase II.

Phase II mixed methods analysis: Researchers will apply a parallel convergent mixed methods design. Quantitative and qualitative data will be collected and analyzed separately, and then paired side-by-side for comparison(10, 11). Quantitative analyses are expected to provide breadth in presenting group-level trends, while qualitative analyses will provide insight into variation within these trends, and allow study participants to identify meaningful SR components for themselves. After independent quantitative and qualitative analyses, the results will be paired side by side for comparison. Researchers will identify and iteratively discuss areas of convergence

SOCIAL PROTOCOL (HRP-580)

PROTOCOL TITLE: A Mobile Informatics Solution to Aid in Memory

VERSION DATE: 7/1/2022

and divergence to validate the results(10-13). The thematic codes and categories of implementation/use and mechanisms of benefit will be cross-tabulated with the empirical data from the randomized controlled evaluation to determine whether the findings diverge, converge, or highlight pathways toward additional questions and analysis(12, 13). This comparative, mixed method analysis approach may suggest how and why PWMCs experience the greatest benefit while using the SRS.

17.2 Power Analysis:

Phase I: The purpose of Phase I is to evaluate feasibility and utility of the SR system, and to identify areas for potential improvement of the technology. The sample size of 20 dyads is appropriate for these objectives.

Phase II: A repeated measures analysis of covariance (ANCOVA) will be utilized to capitalize on the randomized design and the two sets of data that will be collected. The number of PWMC-care partner dyads to be enrolled to address study hypotheses was determined using power analysis procedures(45, 46). A sample size of 100 to identify a medium statistical effect (standardized regression coefficient = 0.15) at a suitable level of statistical power (0.80 is considered an excellent power value) is able to effectively incorporate up to 6 baseline covariates that vary significantly across the randomly assigned Smartwatch Reminder treatment and control conditions if they exist (as random assignment is often used to ensure statistically comparable treatment and control conditions, we feel this is a conservative estimate of baseline covariates)(46). Specifically, we relied on statistical power tables by the expert statistician Cohen(46) to conduct our assessment of power. As noted in Table 2 of Cohen (1992)(45), an alpha level of .05, a medium effect size of .15 (as opposed to using specific measures, Cohen operationalized a medium effect size of .15 as one that is observable, and a survey across the social sciences suggested that this proposed effect size was close to the average of observed effects), and a multiple regression model (similar to an ANCOVA) that includes up to 6 covariates requires a sample size of 97. For these reasons, an expected sample size of 100 PWMC and care partner dyads will be sufficient to conduct the Phase II efficacy evaluation. We anticipate having less than a 3% attrition rate which will ensure we maintain sufficient power. As noted in various recommendations for mixed methods sampling, 20 participants is considered an adequate sample size for semi-structured interview protocols to ensure the richness and depth of open-ended data collected(36, 47).

17.3 Statistical Analysis:

Statistical analyses used will include calculation of frequencies, bivariate correlations, t-tests, chi-square tests, and repeated measures ANCOVA as detailed above.

17.3 Data Integrity:

SOCIAL PROTOCOL (HRP-580)

PROTOCOL TITLE: A Mobile Informatics Solution to Aid in Memory

VERSION DATE: 7/1/2022

Several steps will be taken to ensure data quality. The psychometric properties of the study measures are generally well-established; however, additional steps will be taken to ensure the reliability and validity of the study measures. For example, internal reliability will be established with Cronbach's alpha (α) estimates for each measure and subscale. In addition, construct validity will be comprehensively assessed with a confirmatory factor analysis. In this particular method, individual items of each measure are loaded onto their latent construct. Indices of fit in structural equation models (e.g., Root Mean Square Error of Approximation = .05, Goodness of Fit Index = .97, Non-Normative Fit Index = .93 and Comparative Fit Index = .97; 'excellent' fit is demonstrated in models where $p > .05$, $RMSEA < .05$, $GFI > .92$, $NNFI > .95$ and $CFI > .95$)(32) then act as tests of significance for the construct validity of each measure. These procedures will help to establish the psychometric qualities of each tool beyond their utilization in prior study. Each outcome variable will be examined to determine if skewness exists or outliers are present. Normal probability plots and histograms of each dependent variable will be analyzed; this step is necessary because individual outcome variables must have near-normal distributions in order to be included in subsequent models. If the outcome variables are not normally distributed, the original variables can be subjected to algebraic transformations or other standard transformation techniques to meet model assumptions(9).

18 Health Information and Privacy Compliance

18.1 Select which of the following is applicable to your research:

- My research does not require access to individual health information and therefore assert HIPAA does not apply.
- I am requesting that all research participants sign a HIPCO approved HIPAA Disclosure Authorization to participate in the research (either the standalone form or the combined consent and HIPAA Authorization).
- I am requesting the IRB to approve a Waiver or an alteration of research participant authorization to participate in the research.

Appropriate Use for Research:

- An external IRB (e.g. Advarra) is reviewing and we are requesting use of the authorization language embedded in the template consent form in lieu of the U of M stand-alone HIPAA Authorization. Note: External IRB must be serving as the privacy board for this option.

18.2 Identify the source of Private Health Information you will be using for your research (Check all that apply)

SOCIAL PROTOCOL (HRP-580)

PROTOCOL TITLE: A Mobile Informatics Solution to Aid in Memory

VERSION DATE: 7/1/2022

- I will use the Informatics Consulting Services (ICS) available through CTSI (also referred to as the University's Information Exchange (IE) or data shelter) to pull records for me
- I will collect information directly from research participants.
- I will use University services to access and retrieve records from the Bone Marrow Transplant (BMPT) database, also known as the HSCT (Hematopoietic Stem Cell Transplant) database.
- I will pull records directly from EPIC.
- I will retrieve record directly from axiUm / MiPACS
- I will receive data from the Center for Medicare/Medicaid Services
- I will receive a limited data set from another institution
- Other. Describe:

18.3 Explain how you will ensure that only records of patients who have agreed to have their information used for research will be reviewed: N/A, not reviewing records

18.4 Approximate number of records required for review:

N/A

18.5 Please describe how you will communicate with research participants during the course of this research. Check all applicable boxes

- This research involves record review only. There will be no communication with research participants.
- Communication with research participants will take place in the course of treatment, through MyChart, or other similar forms of communication used with patients receiving treatment.
- Communication with research participants will take place outside of treatment settings. If this box is selected, please describe the type of communication and how it will be received by participants.

Participants will be communicated with via telephone, Zoom, mail, and email. As part of the consent form, participants will agree or not to use unencrypted email for communication throughout the study. If a participant requests the use of encrypted emails, we will do so. PHI will not be sent to participants via any form of communication.

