3.0 Study Endpoints/Events/Outcomes

3.1 Primary Endpoint/Event/Outcome:

Phase I: Twenty care partners will complete a system review checklist and context of care items in a dyadic interview setting. The intervention will be considered successful if at

SOCIAL PROTOCOL (HRP-580)

PROTOCOL TITLE: A Mobile Informatics Solution to Aid in Memory

VERSION DATE: 7/1/2022

least 75% of participants score an average of 4 (out of 5) points or higher on the checklist, indicating that SR met their needs (i.e., indicated agree or strongly agree that the SR was useful, acceptable, and feasible overall). This threshold has been used as a benchmark for success in prior research evaluating technological interventions for PWMC and their care partners(6-8). If the criteria for success are not met, the technology will be refined based on feedback and suggestions from PWMC and care partners, before conducting additional testing with the improved prototypes. Ample qualitative feedback will be available via the dyadic interviews to guide such refinement.

Phase II: Baseline and 6 month data will be used in a 2x2 repeated measures analysis of covariance to examine whether use of the SR results in statistically significant changes in PWMC negative health transitions and , social interaction, pleasant events, social stress, loneliness, relationship closeness, and community engagement and care partner well-being, such as social support, depression and burden (9). The primary independent variable in the proposed investigation consists of an indicator variable for random assignment into the SR treatment condition or the attention control group. Additional analyses will determine if covariates (context of care, mobile device proficiency, and dementia severity indicators) significantly vary across the SR treatment and attention control groups at baseline and over 6-months. If statistically significant variations between the SR treatment and control groups are found, baseline and/or change scores for these covariates will be included in all repeated measures analyses of covariance tests to provide additional statistical control.

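### Baseline covariates enter the Phase II models only if they differ significantly between randomised arms, so chance imbalance, not prognostic value, decides the adjustment

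*Combined protocol and SAP*

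**What the plan says.** The Phase II efficacy analysis compares baseline with 6 months. Section 17.1: "Data available at baseline and 6 months will allow for a 2x2 repeated measures analysis of covariance". The arm indicator is the primary independent variable.

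Covariate adjustment is conditional. Section 17.1 sets the screen: "Additional analyses will determine if covariates (context of care, mobile device proficiency, and dementia severity indicators) significantly vary across the SR treatment" and control arms, both at baseline and over the 6 months. Section 3.1 (repeated in 17.1) gives the consequence: "If statistically significant variations between the SR treatment and control groups are found, baseline and/or change scores for these covariates will be included" in all the repeated measures models. Section 17.2 sizes the trial for "up to 6 baseline covariates that vary significantly across the randomly assigned Smartwatch Reminder treatment and control conditions if they exist".

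No section names a baseline covariate that will be adjusted for whatever the screen shows. No significance level is given for the screen, and there is no rule for the case where more than six covariates pass. Section 5.2 describes randomisation from a list prepared in advance and mentions no stratification.

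**The concern.** With correct randomisation, any baseline difference between arms has arisen by chance. Testing it answers a question whose answer is already known. The question that matters for adjustment is how strongly the covariate predicts the outcome, and the between-arm p-value carries no information on that.

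Three things follow.

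- Each covariate has the same 5% chance of entry (at a 0.05 screen), whether it is strongly prognostic or irrelevant.
- A predictor imbalanced at, say, p = 0.10 is ignored, although adjusting would remove the distortion it causes in that trial.
- One chance flag changes every Phase II outcome model, so nobody can write down the efficacy model before seeing the data.

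At stake are the prespecification of the main analysis, some precision, and the estimate in those trials where a predictive covariate happens to be moderately imbalanced.

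**Working it through.** **Inputs from the documents.** 100 dyads, 1:1, so 50 per arm (Section 5.2). The power calculation in Section 17.2 uses "an alpha level of .05, a medium effect size of .15", power 0.80 and up to six covariates, and requires N = 97. The candidate covariates are described in Section 5.2.

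**Assumptions not in the documents.** A 0.05 level for the screen; a true effect of 0.5 SD; a baseline-to-6-month correlation ρ of 0.5 to 0.8; covariate correlations and R² as stated below.

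**1. The plan's own figure.** For an overall F test with six predictors, f² = 0.15 and noncentrality 0.15 × N, power is 0.798 at N = 97, 0.804 at 98 and 0.813 at 100. The stated 97 is reproduced to within one dyad.

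**2. Chance of at least one false flag.** Twelve non-demographic candidates can be counted in Section 5.2:

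- Context of care (5): location, time since diagnosis, diagnosis type, Medicaid status, living arrangement.
- Dementia severity (5): ADL, IADL, memory impairment scale, recognition item, TICS-40.
- Mobile device proficiency (2): MDPQ-16 for the care partner and for the person with memory concerns (PWMC).

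For K independent candidates the chance is 1 − 0.95^K:

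| K | Chance of at least one flag |
|---|---|
| 3 | 14% |
| 6 | 26% |
| 10 | 40% |
| 12 | 46% |

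The five dementia-severity measures are surely correlated, so 46% is an upper-end value for this list.

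**3. Bias left by moderate imbalance.** The standard error of a covariate mean difference is √(2/50) = 0.20 covariate SD. Consider trials where the covariate favours SR by 1 to 1.98 SE, just short of significance:

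- Share of trials: Φ(1.98) − Φ(1) = 0.135, with the same share in the other direction.
- Mean imbalance in that band: [φ(1) − φ(1.98)] / 0.135 = 1.378 SE, or 1.378 × 0.20 = 0.276 SD.

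The 2x2 arm-by-time test is a test of change. If the covariate correlates a with the baseline outcome and b with the 6-month outcome, its slope on change is b − a, and the bias left by not adjusting is 0.276 × (b − a).

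**4. Power and type I error in the planned change analysis.** Simulation of 100,000 trials per row, one covariate, ρ = 0.6:

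| a, b | Bias in the band (SD) | Power: never / gated / always adjusted | Gated type I error |
|---|---|---|---|
| 0.5, 0.5 | 0.00 | 0.79 / 0.79 / 0.79 | 0.051 |
| 0.4, 0.5 | 0.03 | 0.79 / 0.79 / 0.79 | 0.050 |
| 0.3, 0.5 | 0.06 | 0.79 / 0.79 / 0.81 | 0.050 |
| 0, 0.5 | 0.14 | 0.79 / 0.80 / 0.91 | 0.042 |

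The last row is an extreme: the covariate is unrelated to the outcome at baseline but correlates 0.5 with the same outcome six months later.

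**5. Six candidates together.** Simulation of 6,000 trials per setting, change analysis, six independent candidates with joint R² given the baseline outcome. Power is shown as gated / always adjusted:

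| ρ | R² = 0.10 | R² = 0.20 |
|---|---|---|
| 0.5 | 0.69 / 0.71 | 0.70 / 0.74 |
| 0.6 | 0.79 / 0.80 | 0.80 / 0.84 |
| 0.7 | 0.89 / 0.90 | 0.89 / 0.92 |
| 0.8 | 0.97 / 0.98 | 0.98 / 0.99 |

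Always adjusting gains about 1 point at R² = 0.10 and about 1 to 4 points at R² = 0.20. Gated type I error is 0.042 to 0.049.

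**The case against.** The strongest reply is that the practical effect is small. The planned model always contains the outcome's own baseline value. Cognition, daily function, living arrangement and device proficiency are fairly stable traits, so much of what they share with the 6-month outcome they also share with the baseline outcome, and that part cancels in a change analysis. Nothing in the documents shows that any candidate predicts change, and the TICS-40 is restricted by eligibility to scores of 6 to 24 (Section 9.3). This stands, and it limits the size of the point.

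A reader might infer two stronger things, neither of which the documents support.

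- *That most of the available precision is lost.* A comparison of 6-month scores alone, with a covariate correlated 0.5 with the outcome, gives power of 0.70 under the gated rule and 0.81 if always adjusted. That is not the planned analysis. In the change analysis a gap of that size appears only in the extreme row of step 4. The documents give no correlation, SD or R² from which to fix the loss.
- *That the false-positive rate is inflated.* Across the settings checked it is about 4 to 5%, so nominal or slightly conservative.

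The reply does not rescue the rule. A small expected cost is no reason to let chance choose the model, and no other section supplies a fixed covariate set.

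**Conclusion.** The defect is in the entry rule, and it is explicit in Sections 3.1, 17.1 and 17.2. Adjustment for baseline covariates follows chance imbalance, and the efficacy model is not prespecified. This conclusion needs no assumption beyond randomisation.

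The numerical consequences do rest on assumptions. The chance of at least one false flag is at most about 46% for the 12 candidates (independence, 0.05 screen) and 26% for six independent ones. The power forgone is probably about 0 to 4 points. The bias left in a trial with moderate imbalance is 0 to about 0.06 SD when the covariate is also related to the baseline outcome (the first three rows of step 4), and up to 0.14 SD at the extreme. Overall type I error is not inflated.

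This should be changed because it is a prespecification fault with an easy remedy, not because the trial's result is likely to turn on it. The same sentence also admits change scores measured after randomisation; that is a separate matter and is not assessed here.

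**What to change.** In Sections 3.1, 17.1 and 17.2:

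- Delete the between-arm significance test as the entry rule for baseline covariates.
- Name a short fixed list of baseline covariates, chosen by the sponsor on prognostic grounds before outcome data are seen. Examples already collected are the screening TICS-40 score, living arrangement (PWMC living with the care partner, yes or no) and the PWMC's baseline MDPQ-16.
- State that this list enters every Phase II outcome model whatever the observed balance.
- Report baseline balance descriptively by arm, without p-values.

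The cost is protocol wording and about three degrees of freedom, within the six covariates that Section 17.2 already allows for. No new data are needed. If the chosen covariates turn out not to predict change, there will be little or no gain in power; the benefit is then a model that is known in advance.
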